# List of General Abbreviations/Terminology

НО	Heterotopic Ossification
CRF	Case Review Form
IRB	Institutional Review Board
LAR	Legally Authorized Representative
PI	Principal Investigator
XRT	External Beam Radiation
STC	University of Maryland R Adams Cowley Shock Trauma Center
RCT	Randomized Controlled Trial

#### PROTOCOL SUMMARY

Title	External Beam Radiotherapy as Prophylaxis for Heterotopic Ossification After Surgical Fixation of Acetabular Fractures: a Prospective, Randomized Feasibility Study
Short Title	HO Prophylaxis
Type of Study	Pilot RCT study
Primary Objective	To determine severe HO formation (Brooker class III-IV) between XRT versus no XRT.
Sample Size	100
Diagnosis and Main Inclusion Criteria	Patients 18+ with an acetabular fracture requiring surgical intervention amenable to XRT.
Length of Follow-up	3 months post-operative

#### **Introduction**

Heterotopic ossification (HO) is a common complication after surgical fixation of acetabular fractures, with incidence reported as high as 90%. HO can be a debilitating complication and surgical excision for more severe cases carries a high complication rate. Numerous strategies have been employed to prevent HO formation, but results are often conflicting, and the optimal treatment strategy remains controversial.

The most common interventions used to prevent HO formation are oral administration of indomethacin or single-dose external beam irradiation therapy (XRT). Despite the common use of indomethacin and observational data to support its use, more recent randomized controlled trials (RCTs) have failed to demonstrate any significant reduction in the incidence of severe HO when patients were administered 6 weeks of indomethacin versus placebo. In contrast, XRT has been shown to be effective against HO formation but there remain concerns surrounding the cost and potential long-term effects of XRT. Other authors have described debridement of the gluteus minimus muscle as a primary form of prevention, but the severe HO rate in the largest series of this approach (12%) is higher than that of numerous series that administered XRT as prophylaxis (1-5%).

Given the high incidence of HO, the impact of severe HO on outcomes, and the controversy regarding prophylaxis methods, there remains a need for randomized controlled trials (RCT) to determine optimal strategies for HO prophylaxis. The primary aim of this study is to assess the effect of XRT in preventing severe HO after acetabular surgery.

#### **Study Objectives**

This pilot RCT will determine the effect of external beam radiation (XRT) on preventing severe heterotopic ossification (HO) after acetabular surgery.

#### **Study Design**

This prospective pilot RCT will enroll 100 patients 18 years and older with an acetabular fracture requiring surgical intervention. Patients will be randomized to receive XRT or no XRT post-operatively.

#### **Methods**

#### Setting

Patients will be enrolled at the University of Maryland STC and Emery University. Each clinical site will require local IRB approval. The PI at STC will provide oversight and guidance for the trial and regulatory requirements.

#### **Eligibility** Criteria

The inclusion criteria are:

- 1. Ages 18+
- 2. Acute acetabular fracture
- 3. Indicated for surgical fixation via a posterior or combined anterior and posterior approach

The exclusion criteria are:

- 1. Contraindication to radiotherapy, such as history of cancer/RT
- 2. Patient is getting an acute total hip arthroplasty at the time of fixation of the acetabular fracture.
- 3. Patient is currently pregnant or breastfeeding.
- 4. Patient is likely to have difficulty returning for post-operative follow-ups (i.e. homeless, incarceration)
- 5. Patient does not speak English.

HO Prophylaxis - Protocol v1 (2021.01.22)

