#### Recruitment Strategy, Patient Screening, and Consent

All patients 18 years or older presenting to the hospital with an acute acetabular fracture indicated for surgical fixation will be screened for eligibility by local research staff in close coordination with surgeons and relevant medical staff. Research staff will review the daily orthopaedic trauma census and confirm eligibility by reviewing patient medical records. The PI will be available to answer questions regarding study eligibility. When the PI is not available, any questions will be forwarded to available medical personnel or designated research team member. Surgeons must be willing to participate and have their patients enrolled. Once eligibility has been confirmed, the informed consent process will be completed by research staff with surgeon assistance if possible. Patients will be approached in person by study staff prior to surgery or immediately after about potential participation in the study, whichever is most feasible following determination of eligibility.

*Legally Authorized Representative Consent:* This study will include vulnerable patients incapable to give informed consent. For these individuals we will obtain consent from a legal authorized representative (LAR). The choice of LAR will follow standard procedures. The following with be approached in this order of priority:

- Legal guardian
- Proxy (health care agent) named in an advance directive or durable power of attorney for health care;
- Family member or other surrogate identified by the state law on health care decisions.

Patients, family members, and/or authorized representatives will be included in all study-related discussions and at the time of consent, they will be reminded that all participation is voluntary and the alternative is not to participate. During this consent process, we will review the study and consent forms, and use an Evaluation to Sign Consent Form asking questions based on the study to assess their full understanding and comprehension of what we are asking.

If/when the patient recovers and is able to provide consent for him or herself, we will repeat the consent process with the patient to ensure he or she is still willing to participate.

Randomization: Once consented, eligible patients will be randomized by study staff to XRT versus control. Randomization will be a 50/50 chance, like the flip of a coin. Randomization will occur in REDCap.

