Trial Interventions: Both arms will receive gluteus minimus debridement in the OR, which is considered the standard of care. If randomized to the treatment group, patients that undergo surgical fixation of an acetabular fracture via a posterior or combined anterior and posterior approach will undergo a single fraction of external beam radiotherapy to the surgical site within 72 hours of surgery. This treatment is currently the standard procedure performed for all patients who undergo a posterior or combined approach. The control treatment arm will only include gluteus minimus debridement in the OR and will not receive XRT.

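### Patients can be randomized before surgery on a planned approach, so those whose operation changes stay in the intention-to-treat set and dilute the XRT comparison

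*Combined protocol and SAP*

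**What the plan says.** The approach criterion in the Eligibility Criteria describes a plan: "Indicated for surgical fixation via a posterior or combined anterior and posterior approach". The same section excludes a patient if "Patient is getting an acute total hip arthroplasty at the time of fixation of the acetabular fracture".

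The section on recruitment, screening and consent has staff work with surgeons and "confirm eligibility by reviewing patient medical records". On timing it states: "Patients will be approached in person by study staff prior to surgery or immediately after about potential participation in the study". Allocation then follows consent: "Once consented, eligible patients will be randomized by study staff to XRT versus control". The ratio is 1:1 ("Randomization will be a 50/50 chance, like the flip of a coin"). Nothing ties allocation to a completed operation.

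The Trial Interventions paragraph directs XRT, within 72 hours of surgery, to treatment-group "patients that undergo surgical fixation of an acetabular fracture via a posterior or combined anterior and posterior approach". That is a fact about the operation performed. It also states: "Both arms will receive gluteus minimus debridement in the OR, which is considered the standard of care".

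The Statistical Analysis section makes intention to treat primary and adds an as-treated sensitivity analysis that sorts patients by the prophylaxis they received. No section says what happens when a randomized patient's operation differs from the one planned. No blinding of the surgeon is described.

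**The concern.** Entry depends on the planned operation, while delivery of XRT depends on the operation performed. For a patient randomized before surgery the two can differ.

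- **Anterior-only approach.** The plan directs no XRT for this patient in either arm, so an XRT assignment and a control assignment lead to the same care.
- **Unplanned total hip arthroplasty.** The patient now has a feature the plan excludes, but was allocated before it was known.

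Both stay in the primary analysis. With about 11.5 severe HO events expected in total, and a sample size with no stated allowance for such cases, there is little room for dilution.

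A second consequence has the same cause. If the assignment is known before the incision, it can influence what the surgeon does, including how debridement is carried out. Any such influence could differ by arm, which would be more than dilution.

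**Working it through.** **Inputs.** From the Sample Size section: 100 patients, control rate 20%, an 88% reduction in odds (odds ratio 0.12), two-sided alpha 0.05, stated power 80%. From the 1:1 ratio: 50 per arm.

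**Reproducing the stated power.** Control odds are 0.20/0.80 = 0.25. XRT odds are 0.12 × 0.25 = 0.03, so the XRT rate is 0.03/1.03 = 2.91%. Expected events are 50 × 0.20 + 50 × 0.0291 = 10 + 1.46, about 11.5.

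Two-proportion normal approximation with unpooled variance:

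- SE = √[(0.20 × 0.80 + 0.0291 × 0.9709)/50] = 0.0614
- Power = Φ(0.1709/0.0614 − 1.96) = Φ(0.825) = 79.5%

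This agrees with the stated 80%, so the concern does not rest on a wrong figure.

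**Adding patients whose operation changed.** Let f be their share, equal in both arms, and r their severe HO risk, with no XRT effect in them. The arm rates become (1 − f) × 0.20 + f × r and (1 − f) × 0.0291 + f × r. The documents give neither f nor r, so both are assumptions. For r, 0% and the planned control rate of 20% are used to show a range.

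| f | r | Control rate | XRT rate | Odds ratio | Power, 50 per arm | Total N for 80% |
|---|---|---|---|---|---|---|
| 0% | – | 20.0% | 2.91% | 0.120 | 79.5% | 102 |
| 5% | 0% | 19.0% | 2.77% | 0.121 | 77.0% | 108 |
| 10% | 0% | 18.0% | 2.62% | 0.123 | 74.3% | 116 |
| 5% | 20% | 20.0% | 3.77% | 0.157 | 73.6% | 118 |
| 10% | 20% | 20.0% | 4.62% | 0.194 | 67.3% | 136 |

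Worked row (f = 10%, r = 20%): the XRT rate is 0.9 × 0.0291 + 0.1 × 0.20 = 0.0462, the difference is 0.1538, and SE = √[(0.16 + 0.0462 × 0.9538)/50] = 0.0639. Power = Φ(0.1538/0.0639 − 1.96) = Φ(0.447) = 67.3%.

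**Whether exclusion alone would repair this.** Removing these patients leaves 47.5 or 45 per arm at the original rates, with power 77.5% or 75.2%. When r = 0% that gains less than one point over keeping them (77.0% and 74.3%). When r = 20% it gains more (from 73.6% and 67.3%). Only replacing them so that 100 qualifying patients are randomized restores 79.5%.

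**Whether the planned sensitivity analysis covers it.** The as-treated analysis groups patients by prophylaxis received. An anterior-only patient assigned to XRT but not irradiated would move to the no-XRT group and stay in the analysis. Neither the approach performed nor an arthroplasty is used to sort patients.

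**The case against.** The strongest reply is that the gap is narrow. Eligibility is confirmed from medical records with surgeon input, only eligible patients are randomized, and acute arthroplasty is already an exclusion. For a patient approached after surgery, the approach and any arthroplasty are already known. The gap is therefore confined to allocation before surgery followed by a change of operation. All of this stands, and a reader who infers that the plan never checks eligibility, or that such patients are shown to be in the trial, goes beyond the text. The documents permit these cases but do not say how often they arise.

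A reader might also infer that the comparison holds only if every operation goes as planned. It does not depend on that: intention to treat still compares the assigned strategies, and changes unrelated to assignment dilute the effect without invalidating it.

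A third tempting reading is that controls without debridement would inflate the apparent XRT effect. When allocation follows surgery, an omission precedes it and falls on both arms equally in expectation, so counting it only in controls is wrong. Debridement is a prescribed co-intervention; its omission is a deviation, and making it an entry criterion would be a design preference.

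Finally, the loss is modest beside the choice of test: with no changed operations, exact power is 69.4% for Fisher's test and 82.5% for the uncorrected Pearson test. That limits the importance of the exact figures but is no reason to keep an avoidable loss.

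**Conclusion.** The concern holds in a limited form. The plan allows randomization before surgery on a planned approach, ties XRT to the approach performed, and keeps a patient whose operation changed in the primary analysis without a stated rule. Relative to 79.5%, the loss of power is 2.5 to 5.9 points at an assumed 5% share and 5.2 to 12.2 points at 10%, depending on the severe HO risk in those patients.

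These figures assume an equal share in both arms and no XRT effect in these patients. The second assumption follows from the text for an anterior-only operation. For an unplanned arthroplasty the plan does not say whether XRT is given, so the dilution could be smaller. The unpooled test is used because it reproduces the plan's figure; the primary analysis is an adjusted logistic regression.

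Influence of a known assignment on the operation is possible under the plan, but nothing in the documents shows that it happens, and its size cannot be estimated from them. This is a cheap improvement to the design rather than a flaw that undermines the trial.

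**What to change.** 1. Leave consent before or after surgery, but release the REDCap allocation only after surgery, once the operative record confirms the existing criteria: posterior or combined approach performed, and no total hip arthroplasty. Since XRT is post-operative and consent after surgery is already allowed, this fits the present design. It also removes the route by which a known assignment could affect the operation.
2. Reconcile the planned-approach wording in the Eligibility Criteria with the performed-approach wording in Trial Interventions.
3. Record before allocation whether gluteus minimus debridement was done, and report omissions by arm as deviations from Trial Interventions, not as a new entry criterion.
4. If any patient is still allocated before surgery, keep intention to treat as primary and prespecify a sensitivity analysis excluding, identically in both arms, those whose operation did not meet the Eligibility Criteria. It should remain secondary, because the exclusion follows randomization and the operation could have been influenced by the assignment.

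The cost is a few REDCap fields, drawn from operative details the plan already collects, and short text changes. A few consented patients will not be randomized and must be replaced to reach 100. Allocation must be released promptly after surgery to fit the 72-hour window the plan states.

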#### Recruitment Strategy, Patient Screening, and Consent

All patients 18 years or older presenting to the hospital with an acute acetabular fracture indicated for surgical fixation will be screened for eligibility by local research staff in close coordination with surgeons and relevant medical staff. Research staff will review the daily orthopaedic trauma census and confirm eligibility by reviewing patient medical records. The PI will be available to answer questions regarding study eligibility. When the PI is not available, any questions will be forwarded to available medical personnel or designated research team member. Surgeons must be willing to participate and have their patients enrolled. Once eligibility has been confirmed, the informed consent process will be completed by research staff with surgeon assistance if possible. Patients will be approached in person by study staff prior to surgery or immediately after about potential participation in the study, whichever is most feasible following determination of eligibility.

*Legally Authorized Representative Consent:* This study will include vulnerable patients incapable to give informed consent. For these individuals we will obtain consent from a legal authorized representative (LAR). The choice of LAR will follow standard procedures. The following with be approached in this order of priority:

- Legal guardian
- Proxy (health care agent) named in an advance directive or durable power of attorney for health care;
- Family member or other surrogate identified by the state law on health care decisions.

Patients, family members, and/or authorized representatives will be included in all study-related discussions and at the time of consent, they will be reminded that all participation is voluntary and the alternative is not to participate. During this consent process, we will review the study and consent forms, and use an Evaluation to Sign Consent Form asking questions based on the study to assess their full understanding and comprehension of what we are asking.

If/when the patient recovers and is able to provide consent for him or herself, we will repeat the consent process with the patient to ensure he or she is still willing to participate.

Randomization: Once consented, eligible patients will be randomized by study staff to XRT versus control. Randomization will be a 50/50 chance, like the flip of a coin. Randomization will occur in REDCap.

Trial Interventions: Both arms will receive gluteus minimus debridement in the OR, which is considered the standard of care. If randomized to the treatment group, patients that undergo surgical fixation of an acetabular fracture via a posterior or combined anterior and posterior approach will undergo a single fraction of external beam radiotherapy to the surgical site within 72 hours of surgery. This treatment is currently the standard procedure performed for all patients who undergo a posterior or combined approach. The control treatment arm will only include gluteus minimus debridement in the OR and will not receive XRT.

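### Randomization follows consent, which may precede surgery, and nothing withholds the arm from the surgeon, so the arm can be known during the debridement that is the control arm's only prophylaxis

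*Combined protocol and SAP*

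**What the plan says.** **Consent (Recruitment Strategy, Patient Screening, and Consent).** "Patients will be approached in person by study staff prior to surgery or immediately after about potential participation in the study", whichever is more feasible. Research staff obtain consent, with the surgeon's help where possible.

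**Randomization (same section).** "Once consented, eligible patients will be randomized by study staff to XRT versus control". Allocation is 1:1 in REDCap. The paragraph gives no time relative to the operation and does not say to whom the result is released.

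**Study Design.** "Patients will be randomized to receive XRT or no XRT post-operatively".

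**Trial Interventions.** "Both arms will receive gluteus minimus debridement in the OR, which is considered the standard of care". For the controls: "The control treatment arm will only include gluteus minimus debridement in the OR and will not receive XRT". The XRT arm also receives one fraction within 72 hours of surgery. The extent of the debridement is not specified.

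**Data Collection and Statistical Analysis.** Operative details are collected, but debridement is not named among them. The logistic model adjusts for head injury, mechanical ventilation, hip dislocation and fracture pattern.

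No section mentions blinding, concealment of the allocation, or withholding the arm from the operating surgeon.

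**The concern.** Debridement is performed by the surgeon in the OR and is meant to prevent the primary outcome; the Introduction describes it as a preventive approach in its own right. A surgeon who knew the arm could, knowingly or not, debride more or less thoroughly because of it. Debridement would then be a co-intervention that differs by arm, and the comparison would no longer isolate XRT.

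The protocol gives some reason to take this seriously. Trial Interventions says XRT is currently the standard procedure for all patients having these approaches. A surgeon who knew that a patient was a control would therefore know that the usual prophylaxis was to be withheld. This is a motive for compensating, not evidence that anyone will.

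The exposure serves no purpose. The arms differ only in a treatment given after surgery, so nobody needs the allocation in the OR.

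**Working it through.** **1. What the order of events allows.**

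| Consent | Earliest randomization under the text | Can the arm be known at debridement? |
|---|---|---|
| Before surgery | Before surgery | Yes; nothing prevents it |
| After surgery | After surgery | No |

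The wording fixes an order (consent, then randomization) but no interval. The documents do not say what share of patients will fall in the first row.

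**2. Can the analysis repair it?** The four covariates describe the patient and the injury, and none measures debridement. Its extent would be a post-randomization variable if the arm were already assigned, so adding it to the model would not be a clean remedy.

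**3. The plan's own power figure.** Inputs from Sample Size: N = 100 (taken as 50 per arm), control rate 20%, 88% reduction in odds, two-sided alpha 0.05.
- XRT odds = 0.12 × 0.20/0.80 = 0.03, so the XRT rate = 0.03/1.03 = 2.91%.
- Unpooled normal: SE = √[(0.20×0.80 + 0.0291×0.9709)/50] = 0.0614. Power = Φ(0.1709/0.0614 − 1.96) = Φ(0.825) = 79.5%, which reproduces the stated 80%.

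**4. Illustration: fuller debridement of known controls.** Assume it lowers the control rate from 20% to 15% in a share *f* of controls and that the XRT rate stays at 2.91%. The control rate is then 0.20 − 0.05*f*. Both the 15% and *f* are assumptions.

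| *f* | Control rate | Risk difference (points) | Unpooled power |
|---|---|---|---|
| 0 | 20% | 17.1 | 79.5% |
| 0.25 | 18.75% | 15.8 | 75% |
| 0.5 | 17.5% | 14.6 | 70% |
| 1 | 15% | 12.1 | 58% |

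For *f* = 1: SE = √[(0.15×0.85 + 0.0291×0.9709)/50] = 0.0558, and Φ(0.1209/0.0558 − 1.96) = Φ(0.206) = 58%.

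**5. Dependence on the test**, from *f* = 0 to *f* = 1.

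| Method | Power at 20% | Power at 15% | Fall (points) |
|---|---|---|---|
| Wald log-odds | 64% | 48% | 16 |
| Pooled normal | 77% | 56% | 21 |
| Unpooled normal | 79.5% | 58% | 21 |
| Chi-square, exact enumeration | 82% | 59% | 24 |
| Fisher, exact enumeration | 69% | 41% | 28 |

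Falls are taken from unrounded values. The Wald row uses SE(log OR) = √[1/(n p₁(1−p₁)) + 1/(n p₂(1−p₂))]. At 20% this gives Φ(2.120/0.912 − 1.96), and at 15% it gives Φ(1.772/0.930 − 1.96). It is closest in form to the planned logistic model but ignores the covariates; no row is the planned adjusted analysis.

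**The case against.** **The harm is conjectural.** It needs consent before surgery, randomization before surgery, disclosure to the surgeon and altered debridement. The documents establish only that the first may occur. Study staff, not surgeons, randomize, and both arms are to receive debridement, so omitting it would depart from the protocol. This stands as a limit on the claim. What remains is that the extent is left open and that nothing breaks the chain.

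**Study Design may already mean post-operative randomization.** Its sentence can be read that way, and the exposure would then disappear. But the word most naturally describes when XRT is given, and the Randomization paragraph ties allocation to consent alone. If later randomization was intended, the fix only makes it explicit.

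**A reader might infer that XRT could be made to look effective when it is not.** If controls were debrided less thoroughly, the contrast would widen. Nothing in the documents supports that direction. Suppose XRT had no effect (20% in both arms) and every control's rate rose to 25%. Two-sided rejection would be 9.2% by the unpooled normal approximation, but only 5.9% by Fisher's test (2.8% with no shift). With half the controls affected, the figures are 6.1% and 3.6%. This is not a basis for claiming a false-positive problem.

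**A reader might also infer that debridement will not be recorded.** The CRF is not shown, and operative details are collected, so that cannot be asserted.

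**Conclusion.** The point holds as a gap in the plan: for patients consented before surgery, the text allows the arm to be known during a co-intervention on the primary outcome. It does not hold as a claim that bias will occur. Whether it occurs, its size and its direction cannot be determined from the documents.

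The power losses illustrate what could be at stake. They rest on an assumed 15% control rate and an assumed share of controls affected. The fall of 16 to 28 points is an upper-end case, since it requires every control to be randomized before surgery, with the arm known and acted upon. With half affected, unpooled power is about 70%. Patients consented after surgery are not exposed.

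The change should be made because the exposure is avoidable at little cost, not because the loss has been shown.

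**What to change.** Keep consent before or after surgery. Revise the Randomization paragraph along these lines: *After consent, once surgery is complete and study staff have re-confirmed eligibility in REDCap, staff will randomize the patient; REDCap will generate and release the allocation only at that point.* Align the Study Design sentence with it.

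Re-confirming eligibility also covers a patient found, after consent, to meet the exclusion "Patient is getting an acute total hip arthroplasty at the time of fixation of the acetabular fracture", if that is decided during the operation. The wording may equally mean only planned arthroplasty.

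Under Data Collection, name whether debridement was done and its extent among the operative details, if the CRF does not already capture them, so that the arms can be compared.

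**Cost.** A few sentences and one REDCap check. Neither arm's treatment changes. There is less lead time to arrange XRT within the existing window, as already applies to patients consented after surgery. A few patients may be consented but not randomized; report their number and the reasons.

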# Sample Size

We will enroll 100 patients across all sites. Enrolling 100 patients will give the study 80% power to detect an 88% reduction in the odds of severe HO using a two-sided alpha level of 0.05. The calculation assumes the rate of severe HO in the control group would be 20%.

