# **Statistical Analysis**

The primary analysis will follow the intention to treat principle, evaluating patients according to the group to which they were randomly assigned. To guard against any imbalances in randomization, the effect of XRT on our study outcomes using logistic regression models will be assessed, which will include a treatment indicator and adjusted for head injury, mechanical ventilation, acetabular hip dislocation, and associated fracture pattern. An as-treated sensitivity analysis will also be performed, in which patients will be evaluated according to the HO prophylaxis they received regardless of the treatment assignment. All analyses will be completed using R Version 4.2.2 (R Foundation for Statistical Computing, Vienna, Austria).

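### Release the allocation only after debridement is finished, and state a site-stratified, blocked scheme: a cheap gain for a two-site, open-label trial

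*Combined protocol and SAP*

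**What the plan says.** Three parts of the combined protocol and SAP bear on this.

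**Timing.** Under Recruitment Strategy, Patient Screening, and Consent: "Patients will be approached in person by study staff prior to surgery or immediately after about potential participation in the study". The Randomization paragraph of that section has patients randomized once they have consented. Trial Interventions has both arms undergo gluteus minimus debridement in the operating room. The XRT arm then has a single fraction within 72 hours of surgery. The same section says XRT is at present the routine procedure after these approaches. The Introduction describes debridement as a preventive method in its own right.

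**Scheme.** The method of allocation is given in two sentences: "Randomization will be a 50/50 chance, like the flip of a coin" and "Randomization will occur in REDCap". Blocks, strata, minimization and concealment are not mentioned.

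**Site.** Setting names two centres: "Patients will be enrolled at the University of Maryland STC and Emery University". Statistical Analysis introduces its logistic model with the words "To guard against any imbalances in randomization". The model holds treatment, head injury, mechanical ventilation, hip dislocation and associated fracture pattern. Site is not among them, and no other analysis by site is described.

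**The concern.** The more important matter is timing. Debridement is a co-intervention aimed at the same outcome as XRT. A surgeon who knows that a patient will not have XRT, where XRT has been routine, may debride more thoroughly. One who knows that XRT will follow may debride less. Such a difference would arise after allocation and because of it. Randomization therefore does not protect against it, and neither does adjustment for baseline patient and injury factors.

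The second matter is smaller. If the allocation is a true coin flip, the arms can by chance be uneven within a site. Surgeons and debridement technique may differ between sites. Image reading may too, since Data Collection does not say who reads the 3-month films. With few expected events, a visible site imbalance would make the realised result harder to interpret, and the planned model has no term for it.

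**Working it through.** **1. Timing, by setting the sections side by side.** Approach is allowed before surgery; randomization follows consent; debridement takes place during surgery. For anyone consented before surgery, the plan lets allocation come before debridement. For anyone consented afterwards, it cannot. The share consented before surgery is not stated. Data Collection lists operative details in general but does not name the extent of debridement. No effect size can be derived from the documents.

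**2. The plan's own power figure.** Inputs from Sample Size: "We will enroll 100 patients across all sites", control rate 20%, two-sided alpha 0.05, 80% power "to detect an 88% reduction in the odds of severe HO".
- Control odds = 0.20/0.80 = 0.25. XRT odds = 0.25 × 0.12 = 0.03. XRT rate = 0.03/1.03 = 2.91%.
- Unpooled two-proportion z-test, 50 per arm: standard error = √(0.20 × 0.80/50 + 0.0291 × 0.9709/50) = 0.0614. Then z = 0.1709/0.0614 − 1.96 = 0.825, so power is 79.5%. The stated 80% is reproduced.
- Exact power of the uncorrected chi-square test at 50:50: 82.5%.

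**3. Power cost of a coin flip.** Exact chi-square power is 77.1% with 60 controls and 40 XRT, and 83.8% with 40 controls and 60 XRT. A split of 60:40 or worse in either direction has probability 5.7%. Weighting the exact power at each split by its Binomial(100, 0.5) probability gives 81.9%, an average loss of 82.5 − 81.9 = 0.6 points.

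**4. Imbalance within a site.** Enrolment by site is not stated, so a range is assumed. P(60:40 or worse) = 2 × P(X ≥ 0.6n), with X ~ Binomial(n, 0.5).

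| Patients at the site (assumed) | P(60:40 or worse) |
|---|---|
| 50 | 20% |
| 30 | 36% |
| 20 | 50% |

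The difference between arms in the share of patients from one site was found from 400,000 simulated coin-flip allocations.

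| Site split (assumed) | P(gap of 10 points or more) | P(gap of 20 points or more) |
|---|---|---|
| 50:50 | 37% | 5.7% |
| 70:30 | 29% | 3.1% |
| 90:10 | 10% | under 0.1% |

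**5. What stratified blocks would give.** With blocks of 4 (illustrative), the arms at one site differ by at most 2 patients. Over two sites the difference is at most 4, which is 52:48 overall.

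**6. Room for a site term.** Expected events = 50 × 0.20 + 50 × 0.0291 = 10.0 + 1.46 = 11.5. The planned model has 5 parameters if each covariate takes one: 11.5/5 = 2.3 events per parameter. Adding site gives 11.5/6 = 1.9. The chance of no event in the XRT arm is (1 − 0.0291)^50 = 22.8%, and the ordinary logistic estimate is then not finite. Site is therefore better handled by design and a stratified method than by one more term.

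**The case against.** **The coin phrase may be lay wording.** It may mean no more than 1:1, and a blocked or stratified list may already sit in REDCap. This stands: the documents do not establish simple randomization. They leave the scheme unstated, and one sentence would settle it.

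**Simple randomization is valid.** A reader might infer that site imbalance confounds the treatment effect. Over repeated allocations it does not bias the unadjusted comparison, and the standard error already allows for it. A reader might also compute a shift of 4 points, from a 20-point gap in site mix times assumed site rates of 30% and 10% (0.20 × 0.20). That holds only if XRT has no effect. With an odds ratio of 0.12 at each site, a 70:30 site split and the higher rate at the smaller site, the risk difference is 13.6 points when balanced and 11.3 or 16.0 when not, a shift of about 2.4. With equal arms, a 20:10 or worse split at a 30-patient site has probability 4.9%. The rates are assumptions throughout.

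**Power is hardly affected.** This stands. Citing only the 60-control split would mislead, because the equally likely 40-control split raises power.

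**The covariates are not meant to repair site imbalance.** This also stands: they are patient and injury factors. The sparse model is a separate problem that would persist under perfect stratification.

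**The surgeon may not learn the arm.** No section says that the surgeon is told before debridement, and debridement is specified for both arms. This limits the point to a possibility. But no section withholds the arm either, and study staff randomize in close coordination with surgeons.

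**Conclusion.** The point holds as a low-cost improvement, led by the timing of allocation. As written, the plan allows the arm to be known before a preventive co-intervention is carried out, and its analysis cannot undo a difference that results. The documents do not show that such a difference will occur, and they give no means of sizing it.

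Site stratification is a secondary gain in precision and credibility. The average power cost of a coin flip is about 0.6 points. The chance of a 60:40 or worse split at one site is 36% if it enrols 30, and 20% to 50% over an assumed 50 to 20 patients. These figures assume true coin-flip allocation. The power figures also take the plan's event rates and assume no missing 3-month films. The documents do not support the stronger conclusion that the coin flip makes the treatment estimate biased or the trial underpowered.

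**What to change.** **Randomization paragraph of the recruitment section.** State that REDCap allocates 1:1, stratified by site, in permuted blocks of randomly varying size that are concealed from the sites, and that the allocation is released only after fixation and debridement are complete. Consent may still be taken before surgery.

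**Statistical Analysis.** Account for site in the primary treatment comparison by a method that suits about 11-12 expected events, for example a site-stratified Mantel-Haenszel or exact analysis. State how this relates to the planned covariate-adjusted logistic model, so that there are not two competing primary analyses.

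**Cost.** A new REDCap list and short amendments to two sections, with no extra patients. Blocked allocation is slightly more predictable than a coin flip in an open-label trial; concealed, varying block sizes limit this. XRT would have to be arranged after surgery, within the plan's own 72-hour window. The plan already allows consent after surgery, so that sequence is one it already accepts. If REDCap already holds a blocked, site-stratified list, that part of the change is one sentence of description.
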